### 11.2.3 Methods for Evaluation of Disease

All measurements should be taken and recorded in metric notation using a ruler, calipers, or a digital measurement tool. All baseline evaluations should be performed as closely as possible to the beginning of treatment and never more than 4 weeks before the beginning of the treatment.

The same method of assessment and the same technique should be used to characterize each identified and reported lesion at baseline and during follow-up. Imaging-based evaluation is preferred to evaluation by clinical examination unless the lesion(s) being followed cannot be imaged but are assessable by clinical exam.

Clinical lesions. Clinical lesions will only be considered measurable when they are superficial (*e.g.*, skin nodules and palpable lymph nodes) and  $\geq 10$  mm in diameter as assessed using calipers (*e.g.*, skin nodules). In the case of skin lesions, documentation by color photography, including a ruler to estimate the size of the lesion, is recommended.

Chest x-ray. Lesions on chest x-ray are acceptable as measurable lesions when they are clearly defined and surrounded by aerated lung; however, CT is preferable.

Conventional CT and MRI. This guideline has defined measurability of lesions on CT scan based on the assumption that CT thickness is 5mm or less. If CT scans have slice thickness greater than 5 mm, the minimum size of a measurable lesion should be twice the slice thickness. MRI is also acceptable in certain situations (*e.g.* for body scans).

Use of MRI remains a complex issue. MRI has excellent contrast, spatial, and temporal resolution; however, there are many image acquisition variables involved in MRI, which greatly impact image quality, lesion conspicuity, and measurement. Furthermore, the availability of MRI is variable globally. As with CT, if an MRI is performed, the technical specifications of the scanning sequences used should be optimized for the evaluation of the type and site of disease. Furthermore, as with CT, the modality used at follow-up should be the same as was used at baseline and the lesions should be measured/assessed on the same pulse sequence. It is beyond the scope of the RECIST guidelines to prescribe specific MRI pulse sequence parameters for all scanners, body parts, and diseases. Ideally, the same type of scanner should be used and the image acquisition protocol should be followed as closely as possible to prior scans. Body scans should be performed with breath-hold scanning techniques, if possible.

FDG-PET. While FDG-PET response assessments need additional study, it is sometimes reasonable to incorporate the use of FDG-PET scanning to complement CT scanning in assessment of progression (particularly possible 'new' disease). New lesions on the basis of FDG-PET imaging can be identified according to the following algorithm:

- (a) Negative FDG-PET at baseline, with a positive FDG-PET at follow-up is a sign of PD based on a new lesion.
- (b) No FDG-PET at baseline and a positive FDG-PET at follow-up: If the positive FDG-PET at follow-up corresponds to a new site of disease confirmed by CT, this is PD. If the positive FDG-PET at follow-up is not confirmed as a new site of disease on CT, additional follow-up CT scans are needed to determine if there is truly progression occurring at that site (if so, the date of PD will be the date of the initial abnormal FDG-PET scan). If the positive FDG-PET at follow-up corresponds to a pre-existing site of disease on CT that is not progressing on the basis of the anatomic images, this is not PD.
- (c) FDG-PET may be used to upgrade a response to a CR in a manner similar to a biopsy in cases where a residual radiographic abnormality is thought to represent fibrosis or scarring. The use of FDG-PET in this circumstance should be prospectively described in the protocol and supported by disease-specific medical literature for the indication. However, it must be acknowledged that both approaches may lead to false positive CR due to limitations of FDG-PET and biopsy resolution/sensitivity.

Note: A 'positive' FDG-PET scan lesion means one which is FDG avid with an uptake greater than twice that of the surrounding tissue on the attenuation corrected image.

PET-CT. At present, the low dose or attenuation correction CT portion of a combined PET-CT is not always of optimal diagnostic CT quality for use with RECIST

measurements. However, if the site can document that the CT performed as part of a PET-CT is of identical diagnostic quality to a diagnostic CT (with IV and oral contrast), then the CT portion of the PET-CT can be used for RECIST measurements and can be used interchangeably with conventional CT in accurately measuring cancer lesions over time. Note, however, that the PET portion of the CT introduces additional data which may bias an investigator if it is not routinely or serially performed.

Ultrasound. Ultrasound is not useful in assessment of lesion size and should not be used as a method of measurement. Ultrasound examinations cannot be reproduced in their entirety for independent review at a later date and, because they are operator dependent, it cannot be guaranteed that the same technique and measurements will be taken from one assessment to the next. If new lesions are identified by ultrasound in the course of the study, confirmation by CT or MRI is advised. If there is concern about radiation exposure from CT, MRI may be used instead of CT in selected instances.

Endoscopy, Laparoscopy. The utilization of these techniques for objective tumor evaluation is not advised. However, such techniques may be useful to confirm complete pathological response when biopsies are obtained or to determine relapse in trials where recurrence following complete response (CR) or surgical resection is an endpoint.

Tumor markers. Tumor markers alone cannot be used to assess response. If markers are initially above the upper normal limit, they must normalize for a participant to be considered in complete clinical response. Specific guidelines for both CA-125 response (in recurrent ovarian cancer) and PSA response (in recurrent prostate cancer) have been published [*JNCI* 96:487-488, 2004; *J Clin Oncol* 17, 3461-3467, 1999; *J Clin Oncol* 26:1148-1159, 2008]. In addition, the Gynecologic Cancer Intergroup has developed CA-125 progression criteria which are to be integrated with objective tumor assessment for use in first-line trials in ovarian cancer [*JNCI* 92:1534-1535, 2000].

Cytology, Histology. These techniques can be used to differentiate between partial responses (PR) and complete responses (CR) in rare cases (*e.g.*, residual lesions in tumor types, such as germ cell tumors, where known residual benign tumors can remain).

The cytological confirmation of the neoplastic origin of any effusion that appears or worsens during treatment when the measurable tumor has met criteria for response or stable disease is mandatory to differentiate between response or stable disease (an effusion may be a side effect of the treatment) and progressive disease.

#### 11.2.3.1 Evaluation of Target Lesions

Complete Response (CR): Disappearance of all target lesions. Any pathological lymph nodes (whether target or non-target) must have reduction in short axis to <10 mm.

Partial Response (PR): At least a 30% decrease in the sum of the diameters of target lesions, taking as reference the baseline sum diameters.

Progressive Disease (PD): At least a 20% increase in the sum of the diameters of target lesions, taking as reference the smallest sum on study (this includes the baseline sum if that is the smallest on study). In addition to the relative increase of 20%, the sum must also demonstrate an absolute increase of at least 5 mm. (Note: the appearance of one or more new lesions is also considered progressions).

Stable Disease (SD): Neither sufficient shrinkage to qualify for PR nor sufficient increase to qualify for PD, taking as reference the smallest sum diameters while on study.

#### 11.2.3.2 Evaluation of Non-Target Lesions

Complete Response (CR): Disappearance of all non-target lesions and normalization of tumor marker level. All lymph nodes must be non-pathological in size (<10 mm short axis).

Note: If tumor markers are initially above the upper normal limit, they must normalize for a patient to be considered in complete clinical response.

Non-CR/Non-PD: Persistence of one or more non-target lesion(s) and/or maintenance of tumor marker level above the normal limits.

Progressive Disease (PD): Appearance of one or more new lesions and/or *unequivocal progression* of existing non-target lesions. *Unequivocal progression* should not normally trump target lesion status. It must be representative of overall disease status change, not a single lesion increase.

Although a clear progression of “non-target” lesions only is exceptional, the opinion of the treating physician should prevail in such circumstances, and the progression status should be confirmed at a later time by the review panel (or Principal Investigator).

#### 11.2.3.3 Evaluation of New Lesions

The finding of a new lesion should be unequivocal (i.e. not due to difference in scanning technique, imaging modality, or findings thought to represent something other than tumor (for example, some ‘new’ bone lesions may be simply healing or flare of pre-existing lesions). However, a lesion identified on a follow-up scan in an anatomical location that was not scanned at baseline is considered new and will indicate PD. If a new lesion is equivocal (because of small size etc.), follow-up evaluation will clarify if it truly represents new disease and if PD is confirmed, progression should be declared using the date of the initial scan on which the lesion was discovered.

#### 11.2.3.4 Evaluation of Best Overall Response

The best overall response is the best response recorded from the start of the treatment until disease progression/recurrence (taking as reference for progressive disease the smallest measurements recorded since the treatment started). The patient's best response assignment will depend on the achievement of both measurement and confirmation criteria.

#### For Participants with Measurable Disease (i.e., Target Disease)

Target Lesions	Non-Target Lesions	New Lesions	Overall Response	Best Overall Response when Confirmation is Required*
CR	CR	No	CR	4 wks Confirmation**
CR	Non-CR/Non-PD	No	PR	4 wks Confirmation**
CR	Not evaluated	No	PR	
PR	Non-CR/Non-PD/not evaluated	No	PR	
SD	Non-CR/Non-PD/not evaluated	No	SD	no prior SD, PR or CR
PD	Any	Yes or No	PD	
Any	PD***	Yes or No	PD	
Any	Any	Yes	PD	

\* See RECIST 1.1 manuscript for further details on what is evidence of a new lesion.  
 \*\* Only for non-randomized trials with response as primary endpoint.  
 \*\*\* In exceptional circumstances, unequivocal progression in non-target lesions may be accepted as disease progression.

Note: Participants with a global deterioration of health status requiring discontinuation of treatment without objective evidence of disease progression at that time should be reported as “*symptomatic deterioration.*” Every effort should be made to document the objective progression even after discontinuation of treatment.

#### For Participants with Non-Measurable Disease (i.e., Non-Target Disease)

Non-Target Lesions	New Lesions	Overall Response
CR	No	CR
Non-CR/non-PD	No	Non-CR/non-PD*
Not all evaluated	No	not evaluated
Unequivocal PD	Yes or No	PD
Any	Yes	PD

\* 'Non-CR/non-PD' is preferred over 'stable disease' for non-target disease since SD is increasingly used as an endpoint for assessment of efficacy in some trials so to assign this category when no lesions can be measured is not advised

#### 11.2.4 Duration of Response

Duration of overall response: The duration of overall response is measured from the time measurement criteria are met for CR or PR (whichever is first recorded) until the first date that recurrent or progressive disease is objectively documented (taking as reference for progressive disease the smallest measurements recorded since the treatment started, or death due to any cause. Participants without events reported are censored at the last disease evaluation).

Duration of overall complete response: The duration of overall CR is measured from the time measurement criteria are first met for CR until the first date that progressive disease is objectively documented, or death due to any cause. Participants without events reported are censored at the last disease evaluation.

Duration of stable disease: Stable disease is measured from the start of the treatment until the criteria for progression are met, taking as reference the smallest measurements recorded since the treatment started, including the baseline measurements.

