## SCHEMA

TNBC – triple negative breast cancer; CNS – central nervous system; SRS – stereotactic radiation to brain metastasis;

- \*D1 of Atezolizumab (A) will be administered 2-7 days before the initiation of SRS.
- Bx1 – Baseline tumor biopsy will be obtained within 28 days of starting Atezolizumab.
- Bx2 – Reassessment biopsy will be obtained between C2D1-C2D21.
- Imaging will be performed at screening within 4 weeks before starting Atezolizumab. Tumor assessments, including brain magnetic resonance imaging and computed tomography of the chest, abdomen and pelvis, will be performed every 6 weeks ( $\pm 1$  week) for the first 24 weeks on treatment, and every 9 weeks ( $\pm 1$  week) thereafter, with additional scans as clinically indicated.
- **Blood samples will be collected within 7 days before starting treatment (baseline), at day 1 ( $\pm 3$  days) of cycle #3, #5, #9, and at progression or off protocol therapy, whichever comes first.**
- **Cerebrospinal fluid collection will be performed at 3 times points (baseline, before cycle 3, and at progression or off protocol therapy, whichever comes first).**

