### 5. TREATMENT PLAN

#### 5.1 Treatment Regimen

Forty-five participants will participate in this open-label, single arm phase II study assessing PFS in patients TNBC and brain metastasis. Participants will receive stereotactic radiation in combination with Atezolizumab (1200mg IV) on day 1 of each 21-day (3 week) cycle. The first dose of Atezolizumab will be administered 2-7 days prior to beginning stereotactic radiation. Treatments will be administered on an outpatient basis.

Regimen Description					
Agent	Premedication; Precautions	Dose	Route	Schedule	Cycle Length
Atezolizumab	Not routinely necessary unless prior infusion reaction.	1200 mg	IV The initial dose of atezolizumab will be delivered over 60 (± 15) minutes. If the first infusion is tolerated, the second infusion may be delivered over 30 (± 10) minutes. If the 30-minute infusion is well tolerated, all subsequent infusions may be delivered over 30 (± 10) minutes.	Day 1, q3w	21 days (3 weeks)

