## **6. DOSING DELAYS/DOSE MODIFICATIONS**

Dose delays and modifications will be made as indicated in the following table(s). The descriptions and grading scales found in the revised NCI Common Terminology Criteria for Adverse Events (CTCAE) version 4.0 will be utilized for dose delays and dose modifications. A copy of the CTCAE version 4.0 can be downloaded from the CTEP website [http://ctep.cancer.gov/protocolDevelopment/electronic\\_applications/ctc.htm](http://ctep.cancer.gov/protocolDevelopment/electronic_applications/ctc.htm).

Dosing interruptions are permitted in the case of medical / surgical events or logistical reasons not related to study therapy (e.g., elective surgery, unrelated medical events, patient vacation, and/or holidays). Participants held for these reasons are required to resume therapy within 3 weeks of the scheduled interruption. The reason for interruption must be documented in the participant's medical record.

If there are dosing delays for any reason, all study assessments are to be delayed in the same fashion, such that that scans and other assessments occur in conjunction with cycles of treatment.

No dose reductions are allowed for atezolizumab.

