- h. CT and/or MRI should be of the chest, abdomen and pelvis. Additional imaging studies (CT neck, plain films, etc.) are permitted as clinically indicated. The same radiographic procedures and technique must be used throughout the study for each patient. Assessments should be done during the last 15-21 days of a cycle, q6weeks for the first 24 weeks (i.e. C2, 4, 6, 8) and then can be reduced to q9 weeks (i.e. C11, 14, 17, etc.) until progression. For those taken off-study for reasons other than progressive disease, tumor measurements should continue to be repeated every 6-12 weeks until progression or beginning a new cancer therapy regimen. Failure to complete restaging after a patient has been taken off protocol therapy will not constitute a protocol violation.
- i. Hematology: hemoglobin, hematocrit, platelet count, RBC count, WBC count, percent and absolute differential count.
- j. Chemistry: sodium, potassium, chloride, bicarbonate, glucose, BUN, creatinine, calcium, total bilirubin, total protein, albumin, ALT, AST, alkaline phosphatase, and LDH.
- k. Beginning with cycle 4, TSH will be done every other cycle on Day 1 (i.e. cycles 4, 6, 8, etc.).
- l. In female subjects of child-bearing potential as defined in the eligibility criteria, serum or urine pregnancy test must be performed within **8 days** prior to initiating protocol therapy
- m. cfDNA is required to be drawn on C1D1, Day 1 of RT, C3D1, C5D1, C9D1, at each restaging visit, and at disease progression or discontinuation of protocol therapy, whichever comes first.
- n. Immune markers will be drawn on C1D1, Day 1 of RT, C3D1, C5D1, C9D1, and at disease progression or discontinuation of protocol treatment, whichever comes first.
- o. Baseline tumor biopsy should be obtained within 28 days of the first dose of Atezolizumab. The C2D1 biopsy should be performed as close to C2D1 as possible but may be collected between C2D1 and C2D21. Both the baseline and C2 biopsy are required for participants with accessible disease outside of the field of radiotherapy. A biopsy at the time of disease progression is optional for subjects who have accessible disease and have achieved an objective response (CR or PR) and/or experienced prolonged stable disease for ≥ 24 weeks.
- p. CSF collection will be performed at baseline, C2 day 15 to day 21, and at disease progression or discontinuation of protocol therapy, whichever comes first (±3 days) in at least 10 participants.

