#### 11.2.5 Clinical Benefit rate

Clinical benefit rate: defined as CR, PR and stable disease (SD)  $\geq$  24 weeks.

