To explore the relationship between correlative endpoints obtained from cerebrospinal fluid (CSF) to genetic alterations detected in the tumor and plasma, patient and disease characteristics, and clinical outcomes, the following analyses are planned: cell-free DNA (cfDNA) from serial CSF samples will be quantified using ultra-low pass whole genome sequencing, evaluated as both a continuous factor, and using the pre-defined threshold of TFX > 10% as a dichotomous variable; whole exome sequencing (WES) will be performed to determine copy number and mutation calls.

For paired assessments of WES of tumoral DNA and CSF at baseline and at time of progression, concordance will be assessed as the proportion of overall agreement using bootstrapped standard error estimates and confidence intervals, and kappa statistics to assess non-zero agreement. The following table shows the true Cohen’s Kappa statistic there will be 80% power to detect given the prevalence of the phenotype, number of paired samples, and using a two-sided alpha = 0.05

Prevalence of	# of paired samples (tumor and CSF)	True Cohen’s kappa
20%	20	0.63
	30	0.53
	40	0.46
30%	20	0.61
	30	0.51
	40	0.44
40%	20	0.60
	30	0.50
	40	0.43

The association of baseline CSF assessments to PFS and OS will be explored using Kaplan-Meier estimation and Cox proportional hazard models, and the association to ORR and CBR will be assessed using logistic models. Serial assessments will be characterized using descriptive statistics, and the association to clinical outcome will be modeled as post-baseline time-varying covariates (PFS and OS) and longitudinal mixed effects models (ORR and CBR). All analyses will be exploratory and hypothesis generating and point estimates will be reported with 95% confidence intervals.

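### For a patient without complete or partial response whose progression is first seen at the week-24 scan, clinical benefit is decided by the scan date: no benefit at day 167, benefit from day 168

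*Combined protocol and SAP*

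**What the plan says.** Two sections together define the clinical benefit rate (CBR).

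- Section 11.2.4 (Duration of Response): "Stable disease is measured from the start of the treatment until the criteria for progression are met". The two response durations in the same section count death as an event and censor at the last evaluation. The SD sentence does neither.
- Section 11.2.5: "Clinical benefit rate: defined as CR, PR and stable disease (SD", the SD part having to last at least 24 weeks. No visit, window or tolerance is named.

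Three places govern when the scan takes place.

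- Section 10 (Study Calendar), footnote h, for body imaging: "Assessments should be done during the last 15-21 days of a cycle, q6weeks for the first 24 weeks (i.e. C2, 4, 6, 8". Footnote g sets the same timing for brain MRI. After Cycle 8 the next listed scan is in Cycle 11.
- The Schema sets imaging every 6 weeks, give or take 1 week, "for the first 24 weeks on treatment, and every 9 weeks" after that.
- Section 6, on dosing delays: "all study assessments are to be delayed in the same fashion".

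A second measure of clinical benefit stands in objective 1.4.6 and Section 13.7. It is the share of patients who are stable or responding in each compartment, judged at 16 and at 24 weeks. Neither place refers to Section 11.2.5 or uses the term CBR.

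**The concern.** SD is a status seen on a scan, but Section 11.2.4 measures its length up to the scan that ends it. Section 11.2.5 then compares that length with a threshold lying inside the permitted range of dates for the week-24 scan. Two patients with the same disease course, both progressing at that scan, can thus be classified in opposite ways because of a day's difference in scheduling. The patient scanned later is counted as benefiting on the strength of the scan that shows progression.

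CBR is an outcome in correlative objectives 1.5.1, 1.5.2, 1.5.5 and 1.5.10, and in Section 13.7, where "the association to ORR and CBR will be assessed using logistic models". Section 11.2.5 is the only definition given for that term. The same rule of SD for at least 24 weeks decides who may have the optional biopsy at progression (Sections 1.1.1 and 9.2.1; calendar footnote o).

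**Working it through.** **Inputs.** Cycle length 21 days (Section 5.1: "day 1 of each 21-day (3 week) cycle"); scans on days 15 to 21 of Cycles 2, 4, 6 and 8; threshold 24 × 7 = 168 days; N = 45 and PFS medians of 2 and 3.5 months (Section 13.2). The documents state no sample size, power or event count for CBR, so there is no such figure to reproduce.

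**The plan's own mapping.** 8 cycles × 21 days = 168 days = 24 weeks, and scans two cycles apart are 42 days = 6 weeks apart. The nominal schedule is consistent.

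**Elapsed day of each scan.** Day d of cycle c lies (c − 1) × 21 + (d − 1) days after first dose.

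| Scan | Day 15 | Day 21 | Weeks |
|---|---|---|---|
| Cycle 6 | 5 × 21 + 14 = 119 | 5 × 21 + 20 = 125 | 17.0 to 17.9 |
| Cycle 8 | 7 × 21 + 14 = 161 | 7 × 21 + 20 = 167 | 23.0 to 23.9 |
| Cycle 11 | 10 × 21 + 14 = 224 | 10 × 21 + 20 = 230 | 32.0 to 32.9 |

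The calendar's week-24 scan is therefore 7 to 1 days short of 168.

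**Other readings of the window.**

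- Counting the first day as day 1: 162 to 168, so the last day just reaches the threshold.
- The calendar's general tolerance of 3 days, if it applies on top: 158 to 170.
- Schema: 168 ± 7 = 161 to 175. Of these 15 permitted days, 8 (168 to 175) are at or beyond the threshold and 7 are not.

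**Classification when progression is first seen on this scan and there was no earlier response.** Day 161 or 167: SD is under 168 days, no benefit. Day 168, 170 or 175: SD is at least 168 days, benefit.

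**Dosing delays.** A 7-day delay after the Cycle 6 scan moves the whole Cycle 8 calendar window to 168 to 174. A 21-day delay moves it to 161 + 21 = 182 to 167 + 21 = 188 days. A progressor at that scan has SD of 26 weeks or more, although last seen stable at 17 to 18 weeks. Section 6.1.1 allows toxicity holds of up to 84 days. A hold of 49 days before the Cycle 6 scan would put even that scan at 119 + 49 = 168 to 125 + 49 = 174 days, with the last stable scan in Cycle 4 (days 77 to 83).

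**Size.** Assumption: exponential bi-compartmental PFS, S(t) = exp(−ln 2 × t / m), with m in days at 30.4375 days per month. The share with an event between nominal weeks 18 and 24 is S(126) − S(168).

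- Median 2 months (m = 60.875): 0.23819 − 0.14765 = 0.0905; × 45 = 4.1 patients.
- Median 3.5 months (m = 106.53): 0.44051 − 0.33518 = 0.1053; × 45 = 4.7 patients.

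Placing the two scans elsewhere in their windows (days 125 and 161, 119 and 167, or 126 and 175) gives 3.7 to 5.6 patients. For scale, S(168) × 45 is 6.6 to 15.1 patients still progression-free at 24 weeks.

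**The case against.** **Section 13.7 already measures status at 24 weeks.** A patient with progression on the week-24 scan would not naturally be called stable or responding then, whatever the scan day. This stands for that measure. It does not cure CBR, because Section 11.2.5 alone defines that term and the two passages are not tied together.

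**The shortfall is not universal.** A reader might infer that no on-schedule scan can reach 24 weeks. That holds only for the calendar window counted in elapsed days. Under the Schema, scans on days 168 to 175 are on schedule. The point is that compliant scans fall on both sides of the threshold.

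**Stable patients are not generally denied credit.** A reader might infer that a patient stable at Cycle 8 with no later scan counts as a failure. The documents do not say so: they give no censoring rule for SD, so the case is undefined. A patient who progresses at Cycle 11 has at least 32 weeks of SD and is counted correctly.

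**The count is generous.** It includes deaths, progression on unscheduled scans, patients already credited with a response, and CNS events, whereas Section 11.2 concerns non-CNS disease. All of this stands. Nor may the 9.1% to 10.5% be read as an expected shift in CBR. That would require every such patient to be reclassified, from all scans before day 168 to all at or after it.

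**Toxicity-driven bias is unproven.** Section 6 also shifts scans for delays such as vacations and elective surgery, and the documents give no delay frequencies. A link with toxicity is possible, not shown.

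**The stakes are low.** CBR carries no alpha, power or decision rule, and Section 13.7 labels the analyses exploratory. That is correct.

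**Conclusion.** The defect holds in a limited form. Sections 11.2.4 and 11.2.5, read together, let the date of the week-24 scan decide whether a progressor without prior response counts as benefiting. Dosing delays can extend this to patients last seen stable well before 24 weeks. The result also conflicts with the status-based measure in Section 13.7 and objective 1.4.6.

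The date arithmetic is exact. The size rests on an exponential curve and the plan's own PFS medians: 9.1% to 10.5% of patients, or 4.1 to 4.7 of 45, as an upper guide for the week-24 scan. Those actually misclassified there would be fewer. An earlier scan delayed past day 168 is not in this count, and the documents offer no basis for estimating how often that would happen.

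Only the exploratory and correlative CBR analyses and the optional progression-biopsy criterion are affected. A reader might infer that progressors become responders. They do not: they would be classed as SD, and extracranial ORR, PFS and OS are unaffected.

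**What to change.** 1. In Section 11.2.5, define SD of at least 24 weeks as no progression up to and including the week-24 assessment, with absence of progression documented on a scan at or after the lower limit of a stated window (for example 23 weeks, or 161 days, from first dose, whatever the cycle number). Progression first seen at that scan is then not benefit. Counting from first dose also covers delayed cycles and patients scanned after stopping treatment.
2. State how patients with no scan at or after that limit are classified.
3. Say whether CBR and the 24-week measure in Section 13.7 and objective 1.4.6 are meant to be the same, and align the wording, including the compartments covered.
4. Reconcile the scan windows in the Schema and in calendar footnotes g and h, and refer the progression-biopsy criterion to the same definition.

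The cost is a few sentences and no new data. CBR may come out slightly lower.
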